2.1.4.2 Adverse events variables

All adverse events (including serious adverse events and adverse events with special interest) will be coded to a lower-level term (LLT), preferred term (PT), high-level term (HLT), high-level group term (HLGT), and associated primary system organ class (SOC) using the version of Medical Dictionary for Regulatory Activities (MedDRA) currently in effect at Sanofi at the time of database lock.

The occurrence of adverse events (including serious adverse events and adverse events with special interest) is recorded from the time of signed informed consent until the end of the study.

Adverse event observation period

- Pre-treatment adverse events are adverse events that developed or worsened or became serious during the pre-treatment period.
- Treatment-emergent adverse events are adverse events that developed or worsened or became serious during the TEAE period (as defined in the observation period in Section 2.1.4).
- Post-treatment adverse events are adverse events that developed or worsened or became serious during the post-treatment period.

Injection site reaction adverse events are identified using MedDRA searches: HLGT "Administration site reactions" and HLTs "Administration site reactions NEC", "Infusion site reactions", "Injection site reactions" and "Application and instillation site reactions" and excluding HLTs "Implant and catheter site reactions" and "Vaccination site reactions".

Hypersensitivity reactions adverse events are identified using MedDRA searches: Angioedema SMQ [Narrow], Severe cutaneous adverse reactions SMQ [Broad], Hypersensitivity SMQ [Broad and Narrow] and excluding PTs related to administration, application, injection and infusion sites. HLT "Anaphylactic Responses" are included in those SMQs

Adverse events of special interest include:

- Pregnancy occurring in a female patient entered in the clinical trial or in a female partner of a male patient entered in the clinical trial.
- Symptomatic overdose (serious or non-serious) with IMP/NIMP.
- Increase (\geq 3 ULN or >2 times the baseline value) in alanine transaminase (ALT).

2.1.4.3 Deaths

The deaths observation period are per the observation periods defined above:

- Death on-study: deaths occurring during the on study observation period.
 - Death pre-treatment: deaths occurring before the first IMP intake;
 - Death on-treatment: deaths occurring during the treatment-emergent adverse event period;
- Death post-study: deaths occurring after the end of the study.

2.1.4.4 Laboratory safety variables

Clinical laboratory data consists of blood analysis, including hematology, clinical chemistry, serum pregnancy test in females of childbearing potential and serum follicle stimulating hormone

(FSH) and estradiol (only in females requiring confirmation of postmenopausal status) and urinalysis. Clinical laboratory values after conversion will be analyzed into standard international units and international units will be used in all listings and tables.

Blood samples for clinical laboratories will be taken at screening visit (Visit 1 - Week - 2) for identifying patients with exclusion criteria or safety consideration include serum pregnancy test will be test at screening visit. Urine pregnancy test at site will be performed at Visit 2 and end of treatment. The laboratory parameters will be classified as follows:

- Hematology,
 - **Red blood cells and platelets**: hemoglobin, hematocrit, mean corpuscular volume, mean corpuscular hemoglobin concentration, mean corpuscular hemoglobin, red blood cell count, platelet count, prothrombin time (expressed as international normalized ratio), activated partial thromboplastin time, sedimentation rate;
 - White blood cells: white blood cell count, neutrophils, lymphocytes, monocytes, basophils, eosinophils;
- Clinical chemistry,
 - Electrolytes: sodium, potassium,;
 - **Renal function**: creatinine, eGFR;
 - **Liver function**: alanine aminotransferase, aspartate aminotransferase, alkaline phosphatase (ALP), total and conjugated bilirubin;
 - **Pregnancy test**: Serum β-human chorionic gonadotropin (all female patients);
- Urine samples will be collected as follows:
 - Urinalysis quantitative analyses: pH, specific gravity, proteins, and glucose.

Technical formulas are described in Section 2.5.1.

2.1.4.5 Vital signs variables

Vital signs include: heart rate (bpm), sitting systolic and diastolic blood pressure (mmHg) as well as body weight (kg).

2.1.4.6 Electrocardiogram variables

Electrocardiogram variables include electrocardiogram (ECG) status (normal, abnormal not clinically significant, abnormal clinically significant).

2.1.5 Pharmacokinetic variables

Not applicable.

2.1.6 Pharmacodynamic/genomics endpoints

Not applicable.

2.1.7 Patient-reported outcome endpoints

The patient reported outcomes (PROs) measures in this study are the Diabetes Treatment Satisfaction Questionnaire (DTSQs and DTSQc versions) and the Hypoglycemic Attitudes and Behavior Scale (HABS).

The Diabetes Treatment Satisfaction Questionnaire Status Version (DTSQs) is a validated questionnaire to assess patient satisfaction with treatment and patient perception of blood glucose control. It consists of 8 items that are answered on a Likert scale from 0 to 6.(2)

Items 1, 4, 5, 6, 7 and 8 are summed to produce a Total Treatment Satisfaction score ranging from 0 (no satisfaction) to 36 (high satisfaction with treatment).

The 2 items of 'perceived frequency of hyperglycemia' (Item 2) and 'perceived frequency of hypoglycemia' (Item 3) are scored separately ranging from 0 (none of the time) to 6 (most of the time).

DTSQs will be administered at baseline, 12 and 24 weeks in the local language.

The Diabetes Treatment Satisfaction Questionnaire Change Version (DTSQc) was developed from the original DTSQ to evaluate the change in treatment satisfaction at a specific time point. The change version has the same 8 items as the status version, with a small alteration to the wording of Item 7. The DTSQc instructions and response options differ from those of the DTSQs to produce measures of relative change in satisfaction rather than measures of absolute satisfaction.(3)..

Items are answered on a Likert scale from -3 to +3, and the sum of the treatment satisfaction scores range from -18 to +18. Positive scores are indicative of improvement in treatment satisfaction, whereas negative scores are indicative of deterioration in treatment satisfaction. A score of 0 represents no change.

The 2 items of 'perceived frequency of hyperglycemia' (Item 2) and 'perceived frequency of hypoqlycemia' (Item 3) are scored from -3 ('much less of the time now') to +3 ('much more of the time now'), meaning negative scores indicate fewer problems with blood glucose levels and positive scores indicate more problems than before.

DTSQc will be administered at 12 and 24 weeks in the local language. At 12 and 24 weeks, DTSQs (status) will be administered before the DTSQc (change).

The HABS (Hypoglycemia Attitudes and Behavior Scale) was recently developed with Type 2 diabetic patients using or not insulin (13). It consists of 14 items within 3 domains measuring anxiety (5 items), confidence (5 items) and avoidance (4 items) related to hypoglycemia.

Items are answered on a Likert scale from 1 (strongly disagree) to 5 (strongly agree), with higher scores indicating high avoidance, confidence and anxiety related to hypoglycemia. (4).

The questionnaire will be administered at baseline, 12 and 24 weeks in the local language.

2.1.8 Health economic endpoints

Not applicable.

2.2 DISPOSITION OF PATIENTS

This section describes patient disposition for both patient study status and the patient analysis populations.

Screened patients are defined as any patients who met the inclusion criteria and signed the informed consent.

Randomized patients consist of all screened patients with a treatment arm allocated and recorded in the interactive voice response system (IVRS)/ interactive web response system (IWRS) database, regardless of whether the treatment kit was used or not.

For patient study status, the total number of patients in each of the following categories will be presented in the clinical study report using a flowchart diagram or summary table:

- Screened patients;
- Screen failure patients and reasons for screen failure;
- Non-randomized but treated patients;
- Randomized patients;
- Randomized but not treated patients;
- Randomized and treated patients;
- Patients who completed the 24-week on-treatment period (patients who have performed visit 20, who did not permanently discontinue treatment and who did not take any rescue medication);
- Patients who did not complete the 24-week on-treatment period;
- Patients who discontinued 24-week on-treatment by main reason for permanent treatment discontinuation;
- Patients who completed the study (patients who have performed visit 20, whatever the treatment duration);
- Patients who did not complete the study (patients who have not performed visit 20);
- Patients who discontinued study by main reason for study discontinuation;

- The randomization strata (screening HbA1c categories [<8.0%, ≥8.0%], use of SU or meglitinides at screening [Yes, No]) assigned by IVRS/IWRS. The discrepancy between the strata assigned by IVRS/IWRS and the information reported on case report form (CRF) will be listed for all randomized patients;
- Status at last study contact.

For all categories of patients (except for the screened and nonrandomized categories) percentages will be calculated using the number of randomized patients as denominator for different treatment groups. Reasons for treatment discontinuation will be supplied in tables giving numbers and percentages by treatment group.

Reasons for treatment discontinuation will be supplied in tables giving numbers and percentages by treatment group. A listing of patients who prematurely discontinued study treatment with further reason provided in free text will be provided.

Kaplan-Meier (KM) plots/estimates of the cumulative incidence of IMP discontinuation due to any reason will be provided. Time to treatment discontinuation is defined as the number of days from the first dose of IMP until the day of treatment discontinuation. All completers are considered as censored observations. The censoring time is the number of days from the first dose of IMP until the last dosing date.

Kaplan-Meier (KM) plots/estimates of the cumulative incidence of IMP discontinuation due to adverse event will be provided. Time to treatment discontinuation is defined as the number of days from the first dose of IMP until the day of treatment discontinuation. All completers are considered as censored observations. The censoring time is the number of days from the first dose of IMP until the last dosing date.Kaplan-Meier (KM) plots/estimates of the cumulative incidence of study discontinuation due to any reason will be provided. Time to study discontinuation is defined as the number of days from the randomization date until the day of study discontinuation. All completers are considered as censored observations. The censoring time is the number of days from the randomization date until the day of study discontinuation. All completers are considered as censored observations. The censoring time is the number of days from the randomization date until the last day of study discontinuation.

All critical or major deviations potentially impacting efficacy analyses, randomization, and drug-dispensing irregularities, and other major or critical deviations will be summarized in tables giving numbers and percentages of deviations by treatment group. Patients excluded from the ITT/PP population will be listed as well as patients with major deviation potentially impacting efficacy analyses not resulting in exclusion from ITT or PP populations. These deviations are listed in the data review and surveillance plan.

Additionally, the analysis populations (Section 2.3) for safety and efficacy are summarized in a table by patient counts on the randomized population:

- Efficacy populations: ITT population; Per-Protocol population,
- Safety population.

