#### 10.3.3 List of criteria for permanent treatment discontinuation

The patients may withdraw from treatment with the IMP if they decide to do so, at any time and irrespective of the reason, or this may be the Investigator's decision. All efforts should be made to document the reasons for treatment discontinuation and this should be documented in the e-CRF.

The patients may withdraw from treatment with IMP in case of the following:

- At patient's own request, ie, withdrawal of the consent for treatment
- If, in the Investigator's opinion, continuation with the administration of IMP would be detrimental to the patient's well-being
- At the specific request of the Sponsor

A patient must withdraw from treatment with IMP in either of the following cases:

- Intercurrent condition that requires discontinuation of IMP
- Pregnancy in female participants
- Necessity to use prohibited therapy (see Section 8.9)

Any abnormal laboratory value will be immediately rechecked for confirmation before making a decision of permanent discontinuation of the IMP for the concerned patient.

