1.3 DETERMINATION OF SAMPLE SIZE

The sample size calculation is based on the primary efficacy variable of HbA1c change from baseline to Week 24.

A sample size of 920 randomized patients (460 randomized per treatment group) ensures that the upper bound of the two-sided 95% confidence interval (CI) for the adjusted mean difference between Toujeo and Tresiba would not exceed a non-inferiority margin of 0.3% with at least 90% power. This calculation assumes a common standard deviation (SD) of 1.4% with a 1-sided

test at the 2.5% significant level and a true difference between Toujeo and Tresiba is zero in HbA1c between the treatment groups.

Calculations were made using nQuery Advisor® Software Version 7.0.

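### The curve for stopping IMP because of an adverse event is called a cumulative incidence but estimated by Kaplan-Meier, with no rule for patients who stop for other reasons

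*SAP*

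**What the plan says.** SAP section 2.2 plans two time-to-event displays for stopping IMP, one for any reason and one for AE. For the second it says "Kaplan-Meier (KM) plots/estimates of the cumulative incidence of IMP discontinuation due to adverse event will be provided".

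The sentences that follow are the same for both curves:

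- Event time: "Time to treatment discontinuation is defined as the number of days from the first dose of IMP until the day of treatment discontinuation". No cause is named.
- Censoring: "All completers are considered as censored observations".
- Censoring time: "The censoring time is the number of days from the first dose of IMP until the last dosing date".

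The same section describes completers of the on-treatment period as "patients who have performed visit 20, who did not permanently discontinue treatment and who did not take any rescue medication". It also plans a crude summary: "Reasons for treatment discontinuation will be supplied in tables giving numbers and percentages by treatment group".

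Reasons other than AEs are expected. Protocol section 10.3.3 lists, among others, "At patient's own request, ie, withdrawal of the consent for treatment", a request by the sponsor, and the need for prohibited therapy. Neither document mentions a competing-risk estimator.

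**The concern.** For the any-reason curve the text leaves little open, because stopping is the event and completing is the censoring. The AE curve adds a third group: patients who stop IMP for another reason. They have not had the event and they are not completers, so the copied text does not cover them.

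The estimator also does not fit its label. A patient who has stopped IMP for another reason can no longer stop it because of an AE. Censoring that patient in a Kaplan-Meier analysis makes the curve describe a setting in which no other reason for stopping exists. The cumulative incidence is the proportion who actually stop because of an AE while other reasons operate.

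At stake is one descriptive tolerability display in an open-label comparison. If the arms differ in non-AE stops, the upward shift differs between arms, and two programmers could handle the uncovered group differently.

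**Working it through.** **Plan's own figure.** There is none to reproduce. The documents state no expected rate of discontinuation, for AE or otherwise, so the rates below are assumptions shown over a range.

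**Inputs**

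- p1 = true 24-week cumulative incidence of AE stops, assumed 1%, 2% or 5%.
- p2 = the same for all other stops, assumed 3% to 20%.
- P = p1 + p2.
- Constant cause-specific hazards over the 24 weeks (assumed).
- 460 patients per arm (SAP section 1.3), used only to judge scale.

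**Formulas**

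1. Total cumulative hazard at Week 24: Λ = −ln(1 − P).
2. AE share of it: Λ × p1/P.
3. Kaplan-Meier with non-AE stops censored targets 1 − exp(−Λ × p1/P) = 1 − (1 − P)^(p1/P).
4. Aalen-Johansen targets p1.

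**One case in full.** With p1 = 2% and p2 = 10%, P = 12% and Λ = −ln(0.88) = 0.1278. The AE share is 0.1278 × 2/12 = 0.0213, and 1 − exp(−0.0213) = 2.11%, against a true 2.00%. A simulation of 4,000 trials with 460 patients gave mean estimates of 2.10% and 1.99%.

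**Range**

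| p1 (AE) | p2 (other) | Aalen-Johansen | 1 − KM, others censored | Excess (points) | Ratio |
|---|---|---|---|---|---|
| 1% | 3% | 1.00% | 1.02% | 0.02 | 1.015 |
| 1% | 20% | 1.00% | 1.12% | 0.12 | 1.116 |
| 2% | 5% | 2.00% | 2.05% | 0.05 | 1.026 |
| 2% | 10% | 2.00% | 2.11% | 0.11 | 1.054 |
| 2% | 20% | 2.00% | 2.23% | 0.23 | 1.117 |
| 5% | 3% | 5.00% | 5.08% | 0.08 | 1.016 |
| 5% | 20% | 5.00% | 5.59% | 0.59 | 1.118 |

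**Between arms.** If both arms have p1 = 2% but one has p2 = 5% and the other 20%, the curves end at 2.05% and 2.23%. That is a spurious difference of 0.18 points.

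**Dependence on timing.** The excess is zero if every AE stop comes before every other stop. It is largest if all other stops come first, when the estimate becomes p1/(1 − p2): 0.02/0.90 = 2.22% for p1 = 2%, p2 = 10%, and 0.05/0.80 = 6.25% for p1 = 5%, p2 = 20%.

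**Scale.** With 460 patients, the binomial standard error is √(0.02 × 0.98/460) = 0.65 points at 2% and √(0.05 × 0.95/460) = 1.0 points at 5%. Every excess in the table is below the corresponding standard error.

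**A second uncovered group.** After rescue, patients continue IMP (Protocol section 8.3.2), but the on-treatment completer definition excludes them. If completer has that meaning in the censoring sentence, a rescued patient who finishes IMP is neither a discontinuer nor a completer and has no stated censoring rule.

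**The case against.** The strongest reply is that this is a gap in the wording of a disposition plot. The event is named as discontinuation due to AE, and most statisticians would censor the other stops without being told. The bias is then smaller than sampling error. SAP section 2.4.5 calls the safety analysis essentially descriptive, and no test uses the curve. The crude figure is available elsewhere: by reason in SAP section 2.2, and as treatment-emergent AEs leading to permanent discontinuation in SAP section 2.4.5.2. Kaplan-Meier with other causes censored is also a legitimate display if labelled as cause-specific.

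All of this stands as a limit on importance. It does not remove the mismatch, since the SAP names a cumulative incidence and the stated estimator does not deliver it under that same usual reading.

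Two stronger readings are tempting and should not be adopted:

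- **Only completers are censored, so every non-AE stop counts as an AE event.** The AE curve would then equal the any-reason curve, for example 12% in place of 2% with p1 = 2% and p2 = 10%. The SAP says that all completers are censored, not that only completers are. This reading also conflicts with the named event and would leave the second curve without a purpose. It could arise only if the copied text were programmed without adaptation.
- **The curve is a key tolerability output that ought to match the disposition table.** It is not among the safety endpoints in SAP section 2.1.4. An exact match is not guaranteed with any estimator, because the table percentages use randomized patients and the curve starts at first dose.

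**Conclusion.** The point holds as a minor one. For the AE curve, SAP section 2.2 has no rule for non-AE stops and uses an estimator that does not give the quantity it names. With those stops censored, the curve is too high by about 0.02 to 0.6 percentage points, or 1.5% to 12% in relative terms. This rests on assumed rates of 1-5% (AE) and 3-20% (other) and on constant hazards; timing could reduce the excess to zero or raise it to the bounds shown. The sample size, primary analysis, type I error and by-reason tables are not affected. The reason to act is that the text should lead to one curve and that curve should be what its title says.

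**What to change.** Replace the copied sentences for the AE curve in SAP section 2.2 with a rule that:

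1. defines the event as permanent IMP discontinuation due to AE, timed from first dose;
2. treats permanent IMP discontinuation for any other reason as a competing event;
3. censors at last dose all patients still on IMP at end of treatment, whether or not they received rescue therapy;
4. estimates the curve by the Aalen-Johansen cumulative incidence function, by arm.

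Keep Kaplan-Meier for the any-reason curve, with the same statement about rescued patients who continue IMP. If Kaplan-Meier is preferred for the AE curve as well, state that other stops are censored and do not title the result a cumulative incidence.

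The cost is a sentence or two in the SAP and a standard SAS procedure or macro. It needs no new data and changes no other analysis.

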2.2.1 Randomization and drug dispensing irregularities

Randomization and drug-dispensing irregularities occur whenever:

1. A randomization is not in accordance with the protocol-defined randomization method, such as a) an ineligible patient is randomized, b) a patient is randomized based on an incorrect stratum, c) a patient is randomized twice, or d) in a dynamic randomization scheme the treatment assignment is, in fact, not random, due to a computer program error.

OR

2. A patient is dispensed an IMP kit not allocated by the protocol-defined randomization, such as a) a patient at any time in the study is dispensed a different treatment kit than as randomized (which may or may not contain the correct-as-randomized IMP), or b) a nonrandomized patient is treated with IMP reserved for randomized patients.

Randomization and drug-dispensing irregularities will be monitored throughout the study and reviewed on an ongoing basis.

All randomization and drug-dispensing irregularities will be documented in the clinical study report. If the number of irregularities is large enough to make a tabular summary useful, the irregularities will be categorized and summarized among randomized patients (number and percentages). Nonrandomized, treated patients will be described separately.

Randomization and drug-dispensing irregularities to be prospectively identified include but are not limited to:

Randomization and drug allocation irregularities
Kit dispensation without IRT transaction
Erroneous kit dispensation
Kit not available
Randomization by error
Patient randomized twice
Forced randomization
Stratification error
Patient switched to another site

2.3 ANALYSIS POPULATIONS

Patients treated without being randomized will not be considered randomized and will not be included in any efficacy population.

Patients who are dispensed study drug without calling the IVRS or before calling the IVRS are considered non-randomized patients. They are excluded from any population for analysis,

including safety. However, if these patients experienced any significant safety event, they should be documented separately in the clinical study report.

The randomized population includes any patient who has been allocated to a randomized treatment regardless of whether the treatment kit was used.

For any patient randomized more than once, only the data associated with the first randomization will be used in any analysis population. The safety experience associated with any later randomization will be assessed separately.

The safety experience of patients treated and not randomized will be reported separately, and these patients will not be in the safety population.

